16.1 Sample size calculation

No formal sample size calculations have been performed. The sample size of 100 completers is based on EMA guideline⁷.

16.2 Definition of analysis sets

Descriptions and analysis of efficacy data will be based on the Full Analysis Set (FAS), as defined in ICH E9 guidelines. ²⁶ The FAS includes all patients exposed to N8-GP. The safety analysis and descriptions will be based on the Safety Analysis Set (SAS). The SAS will consist of all patients exposed to N8-GP.

16.3 Primary endpoint

The primary endpoint is a safety endpoint defined as incidence of inhibitory antibodies against FVIII.

The rate of inhibitory antibodies will be reported and a 1-sided 97.5% upper confidence limit will be provided based on an exact calculation for a binomial distribution. For the calculation of the rate the numerator will include the patients with inhibitors, while the denominator will include all patients with a minimum of 10 exposure days plus any patient with less than 10 exposure days but with inhibitors.

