Novo Nordisk will use the Global Haemophilia Network Investigator Portal to distribute and share trial-related documents and information with the participating sites.

The eDiary software and hardware implementation are compliant with the requirements of FDA 21 CFR Part 11 and ICH E6 (EU directive for personal data protection). After trial completion, each trial site will be supplied with long-life CDs. These CDs will contain site-specific patient records including the patient's eDiaries and audit trail including any data additions and corrections made on each form. The eDiary vendor will furthermore retain and securely store copies of all archived documents and data for 15 years or as required by local data retention laws for trial data.

Protocol v 1 91 of 114

04 November 2013 | Novo Nordisk Protocol Date: Trial ID: NN7088-3908 Version: 1.0 CONFIDENTIAL Final

Status:

92 of 114

Page:

UTN: U1111-1148-1897 EudraCT No.: 2013-004025-88

16

Statistical considerations

Novo Nordisk will be responsible for the statistical analysis.

The main statistical reporting of the trial will be performed when 50 patients have completed main phase (minimum 25 weeks) with at least 50 EDs and completed visit 9. EDs during ITI treatment will not count in the determination of when a patient has reached 50 EDs. Data from patients not yet having completed the main phase and data from patients that have entered extension phase at this point will be included up to latest visit prior to this cut-off date. This report will cover all endpoints, and will form the basis for the paediatric indication. The data will be presented for the main phase and for the extension phase separately as well as combined.

Except for the confidence interval for inhibitor rate and for annualised bleeding rate, the evaluation of data will be based on descriptive statistics, i.e. summary tables, listings and figures.

An updated reporting of the trial with supportive data will be performed when 100 patients have had at least 100 EDs. Data from all patients will be included up to latest visit prior this cut-off date. The data will be presented for the main + extension phase and the extended prophylaxis period (beyond 100 EDs) separately as well as combined.

All data, will be reported separately in a final report when the trial is completed.

[figure not shown]

Figure 16–1 Individual patient flow and time periods for trial reporting

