16.4.2 Supportive secondary endpoints

16.4.2.1 Number of bleeding episodes during prophylaxis

Annualised bleeding rate will be summarised and a 95% two sided confidence interval will be provided based on a negative binomial regression model with number of bleeding episodes requiring treatment with N8-GP as the outcome variable, and adjusting for exposure time. For comparison with previous trial, a sensitivity analysis based on a Poisson regression model allowing for over-dispersion will also be performed.

Since it must be expected that some patients will withdraw, it becomes essential to account for how such withdrawals may affect the analyses of the prophylaxis effect. The analyses above already account for possible different treatment durations by using treatment duration as an offset. This is a proper adjustment if withdrawal is not related to the observed bleeding frequency. However, since it is possible that patients will withdraw exactly because of the observed bleeding rate it is important to perform sensitivity analyses that may account for withdrawn patients possibly being qualitatively different from completing patients.

Specifically this will be done by performing sensitivity analyses for all prophylaxis analyses using a last observation carried forward (LOCF) approach for all patients with at least 1 month prophylaxis treatment duration by calculating the yearly bleeding episode rate for withdrawn patients and use that as an endpoint. As an example a patient with 6 bleeding episodes in 4 months will have an endpoint value of 18 corresponding to a maintained bleeding rate of 18 bleeding episodes per year. For patients withdrawing within 1 month this method is considered to give too uncertain LOCF values, hence imputation will not be attempted for such patients.

Annualised bleeding rate will also be summarised by type of bleeding episode.

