16.5 Interim reporting

An interim efficacy and safety evaluation is planned when approximately 50 patients have reached 25 exposure days. The data will be presented for separately for the main phase and extension as well as combined.

Protocol Amendment no 6 Trial ID: NN7088-3908

CONFIDENTIAL

 Date:
 21 June 2019
 Novo Nordisk

 Version:
 1.0

 Status:
 Final

 Page:
 1 of 4

Protocol Amendment

no 6

to Protocol, version 5 dated 13 June 2019

Trial ID: NN7088-3908

Safety and Efficacy of turoctocog alfa pegol (N8-GP) in Previously Untreated Patients with Haemophilia A

Trial phase: 3a Applicable to Israel

This confidential document is the property of Novo Nordisk. No unpublished information contained herein may be disclosed without prior written approval from Novo Nordisk. Access to this document must be restricted to relevant parties.

IL Protocol Amendment 6 il 1 of 4

Protocol Amendment no 6
Trial ID: NN7088-3908

CONFIDENTIAL

Date: 21 June 2019 | Novo Nordisk

Version: 1.0
Status: Final
Page: 2 of 4

Table of Contents

1	Introduction including rationale for the protocol amendment	3
2	Changes	3

Protocol Amendment no 6
Trial ID: NN7088-3908

CONFIDENTIAL

Date:
21 June 2019
Version:
5 tatus:
Final
Page:
3 of 4

1 Introduction including rationale for the protocol amendment

Patients with congenital haemophilia A have a mutation in coagulation Factor VIII (F8) gene. The different types of mutations in the F8 gene are associated with different probabilities for development of inhibitors. Inhibitors are antibodies that reduce or eliminate the activity of Factor VIII proteins thereby rendering treatment with replacement factor products, such as N8-GP, difficult.

Patients from Israel were excluded from the F8 and Human Leucocyte Antigen (HLA) genotype testing in the previous versions of protocol. However, since the incidence of Factor VIII inhibitors is the primary endpoint of the trial and certain mutations are related to very high inhibitor rates, the mutation composition of the trial population is pivotal for the understanding of the immunogenicity.

Protocol Amendment no 4 version 1.0 dated 14 June 2018 (applicable only for Israel), which has recently been approved by the Health Authorities in Israel introduced F8 and HLA genotype testing for all patients going forward. Protocol Amendment no 4 version 1.0 dated 14 June 2018 was incorporated in protocol version 5 dated 13 June 2019.

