The foremost purpose of this eighth protocol amendment is to finalise the NN7088-3908 trial prior to the milestone of 100 patients achieving 100 exposure days (EDs). Novo Nordisk A/S (NN) would like to maintain the current protocol defined trial end date of 13 November 2021 (LPLV). However, NN has predicted that the trial will not reach the originally targeted 100 patients by the protocol defined end of recruitment date of 02 October 2020. Based on the number of currently recruited patients and the recruitment rate in the trial, it has been predicted that the trial would need to continue at least until Q4 2025 to reach the milestone of 100 patients with 100 EDs. Still, NN expects to have completed the main phase with 50 patients with 50 EDs and V9 by Q3 2020. It has therefore been decided to maintain the planned date of LPLV, but to terminate recruitment of patients into NN7088-3908 with a predicted lower patient number than originally planned. This decision ensures that the paediatric investigation plan (PIP) commitment to EMA is achieved. In addition, PUP trials are no longer an EMA requirement in Haemophilia (https://www.ema.europa.eu/en/documents/scientific-guideline/guideline-clinical-investigationrecombinant-human-plasma-derived-factor-viii-products-revision-2 en.pdf), consequently all regulatory commitments will be met.

On 29 May 2019, the Safety Committee for N8-GP validated a safety signal in the NN7088-3908 trial. The safety signal was related to a transient low incremental recovery (IR) following the initial administrations of turoctocog alfa pegol in the absence of detectable inhibitors in a proportion of previously untreated patients (PUPs) within the first 5 exposure days. The observed low IR was generally transient, and the majority of patients returned to baseline levels over time. To ensure additional insights into the efficacy and safety of N8-GP during low IR periods, an intensified PEG antibody analysis has been implemented. The analysis will be done from blood samples collected for N8-GP binding antibodies. Therefore, no additional blood samples will need to be collected.

Other clarifications to the protocol:

To align the protocol with the most recent monitoring process, which has been simplified to allow for more risk-based monitoring, the protocol has been updated so that monitoring on-site visits can be substituted with remote monitoring when considered feasible.

In this protocol amendment:

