- Any new text is written in italics.
- Any text deleted from the protocol is written using strike through.

Protocol Amendment no 8		Date:	15 June 2020	Novo Nordisk
Trial ID: NN7088-3908	CONFIDENTIAL	Version:	1	
UTN: U1111-1148-1897	CONFIDENTIAL	Status:	Final	
EudraCT no.: 2013-004025-88		Page:	4 of 10	

2 Changes

Following sections in the protocol are affected by this eighth protocol amendment:

1 Summary

[...]

Time frames for evaluation of Objectives/Endpoints

All objectives/endpoints will be evaluated when the first 50 PUPs have reached at least 50 exposure days with V9 dates, when the first 100 PUP have reached 100 exposure dates, and at end of trial. End of trial will be up to 4 years after the *first* patient has reached 100 exposure dates days.

[...]

Trial design:

[...]

The European medical agency requires required submission of safety and efficacy data from minimum 50 exposure days in at least 50 patients for approval of the indication in PUPs, with a post-approval commitment to follow- at least 100 patients for a minimum of 100 exposure days. When the first 50 patients have reached a minimum of 50 exposure days and V9, the analysis and evaluation for the main trial report will be performed. All patients Patients may continue in the extension phase for the purpose of collecting data for a minimum of 100 exposure days in at least 100 patients.

Protocol Amendment no 8
Trial ID: NN7088-3908
Version: 1
CONFIDENTIAL
CONFIDENTIAL
Version: 1
CONFIDENTIAL

UTN: U1111-1148-1897 EudraCT no.: 2013-004025-88 Version: 1
Status: Final
Page: 5 of 10

2 Flow chart

Table 2-1 Flow chart visits and assessments

Visit number	0 ¹	11	2	3	4-6	7-8	9	10-13	14	15-X ¹⁹	EOT
Visit purpose	Screening	Dosing	Dosing	Dosing	Dosing	Dosing	End of main	Dosing	End of extension	Dosing (until EOT)	End of Trial
Time of visit (ED(s)) ²	0	1	2	5	10, 15, 20 3	30,40	50	60, 70, 80, 90	100	NA	
Visit interval (ED(s)) ²		0	0	±1	±2	±2	+2	±2	+2	24w±4w	
CENTRAL LABORATORY ASSESSMENTS											
FVIII activity – trough9	X ⁸	Х		Х	Х	Х	Х	Х	Х	Х	Х
FVIII activity – recovery (30 min post-dose)		Х		Х	х	Х	Х	х	х	х	
N8-GP/FVIII binding antibodies ⁹		х		х	х	х	х	х	х	х	х
PEG antibodies9		Х		X	X	X	Х	X	Х		Х
FVIII inhibitor test ⁹		X ¹⁸		Х	Х	Х	Х	Х	Х	Х	Х
HIV antibodies	(X) ¹⁰										
CD4+ lymphocyte count and HIV viral load	(X) ¹⁰										
Haematology	Х	X ¹¹					Х		Х		Х
Biochemistry	Х	X ¹¹					Х		Х		Х
F8 + HLA genotype testing	(X) ¹²	(X) ¹²									

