8.4.2.2 Antibody assessments

[...]

PEG antibodies

PEG *IgM/IgG* antibodies should be measured according to Table 2–1 and if required, investigator may take additional PEG-antibodies samples at other visits. Samples will be analysed *regularly* for PEG binding antibodies at the end of trial or whenever considered relevant and results will be reported to investigators at the end of trial, or whenever considered relevant, and will be included in the CTR.

[...]

13 Monitoring procedures

[...]

A monitoring visit must be performed as soon as possible after FPFV and no longer than 4 weeks after. The monitoring intervals will depend on the outcome of the remote monitoring of the eCRFs,

Protocol Amendment no 8		Date:	15 June 2020	Novo Nordisk
Trial ID: NN7088-3908	CONFIDENTIAL	Version:	1	
UTN: U1111-1148-1897	CONFIDENTIAL	Status:	Final	
EudraCT no.: 2013-004025-88		Page:	9 of 10	

the trial site's recruitment rate and the compliance of the trial site to the protocol and GCP. The intervals between monitoring visits must not exceed 12 weeks whilst patients are in the trial. at site between V0 and V14. If all patients at site are in the period after V14, intervals between monitoring visits must not exceed 26 weeks, provided site contact at least every 12 weeks.

[...]

16 Statistical considerations

[...]

An updated reporting of the trial with supportive data will be performed when 100 patients have had at least 100 EDs. Data from all patients will be included up to latest visit prior this cut-off date. The data will be presented for the main + extension phase and the extended prophylaxis period (beyond 100 EDs) separately as well as combined.

A final report of the trial will be made after the LPLV cut-off on 13 November 2021. In case some ITI patients haven't finished their treatment at the time of LPLV, an addendum to the final report will be made once the last ITI patient has completed the trial.

All data will be reported separately in a final report when the trial is completed.

CONFIDENTIAL

Date: Version: Status: Page:

15 June 2020 1 Final 10 of 10

Novo Nordisk

[figure not shown]

Figure 16-1 Individual patient flow and time periods for trial reporting

[...]

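### The primary inhibitor rate has only a 10-exposure-day floor, so it is not a risk by a stated number of exposure days, and its exposure basis differs between reports

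*Combined protocol and SAP*

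**What the plan says.** Section 16.3 takes patients with inhibitors as the numerator, and "the denominator will include all patients with a minimum of 10 exposure days plus any patient with less than 10 exposure days but with inhibitors". The interval is an exact binomial one-sided 97.5% upper limit. Section 16.4.2.3 reports the high-titre rate in the same way. No amendment excerpt in the file changes 16.3.

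For the main report, Section 16 includes "Data from patients not yet having completed the main phase and data from patients that have entered extension phase", up to the latest visit before the cut-off. It adds: "The data will be presented for the main phase and for the extension phase separately as well as combined". Section 16.3 does not say which of these presentations carries the primary rate.

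The reporting points are:
- Interim (Amendment 5, Section 16.5): "An interim efficacy and safety evaluation is planned when approximately 50 patients have reached 25 exposure days".
- Main report (Amendment 8, Summary): "All objectives/endpoints will be evaluated when the first 50 PUPs have reached at least 50 exposure days with V9".
- Final report (Amendment 8, Sections 16 and 16.5): "A final report of the trial will be made after the LPLV cut-off on 13 November 2021", with no ED requirement.

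For the secondary bleeding rate, Section 16.4.2.1 does deal with unequal follow-up: "The analyses above already account for possible different treatment durations by using treatment duration as an offset".

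**The concern.** Inhibitor risk in previously untreated patients accumulates with exposure. A proportion that treats every inhibitor-free child past ED 10 as a completed negative depends on how far the children have got when the data are cut. The three reports cut at different stages, so the same product with the same true risk can give different rates in successive reports.

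No decision rule in the plan uses the rate in 16.3. However, Sections 11.6.2 and 16.6 state an expected inhibitor rate of about 30%. Readers will naturally set the result beside that figure and compare the trial's own reports with each other. Neither comparison is like for like unless an ED number is attached.

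**Working it through.** **Plan figures.** Section 16.3 states no numerical rate to reproduce. The one planning figure that can be checked, 125 patients started for 100 completers at 20% drop-out (Section 6.5), reproduces as 100/(1 - 0.20) = 125 and is not in dispute.

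**Step 1: one child.** Assume 30% risk by ED 50, with onset lognormal (sigma 0.7) truncated at ED 50, and let F(12) be the share of onsets by ED 12. The remaining risk for an inhibitor-free child at ED 12 is 0.30 × (1 - F(12)) / (1 - 0.30 × F(12)).

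| Onset median parameter | F(12) | Remaining risk to ED 50 |
|---|---|---|
| ED 8 | 0.722 | 0.0834/0.7834 = 10.6% |
| ED 15 | 0.392 | 0.1825/0.8825 = 20.7% |
| ED 25 | 0.176 | 0.2474/0.9474 = 26.1% |

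Section 16.3 counts this child as a full negative.

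**Step 2: a simple cohort with a different onset curve.** Assume F(t) = 0.30 × (1 - exp(-t/tau)) / (1 - exp(-50/tau)), with tau = 8, 15 or 25 EDs.
- 50 children all at ED 25: expected crude rate 28.7%, 25.2% or 21.9%.
- 50 children all at ED 50: 30.0%.
- 50 at ED 50 plus 20 spread evenly over ED 10 to 49: 20.63/70 = 29.5%, 20.05/70 = 28.6% or 19.56/70 = 27.9%.

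The first line is an extreme, because a real interim would also hold children beyond ED 25. The last is closer to the main report.

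**Step 3: simulation of the reports (18 scenarios, 2,500 trials each).** Inputs from the documents: recruitment from 26 June 2014 to 2 October 2020 (75.2 months), last patient last visit (LPLV) on 13 November 2021 (month 88.6), 20% drop-out, the scheduled visit EDs and the three triggers. Assumed inputs:
- accrual of 1.0 to 1.2 patients per month (75 to 90 patients);
- 65% starting on slow pre-prophylaxis, then 1, 2 or 2.33 EDs per week;
- the Step 1 onset curves, with true risk 30% by ED 50 and 0 or 3 further points by ED 100;
- 60% of inhibitors high titre, with those patients no longer accruing EDs toward the cuts;
- drop-out uniform over ED 1 to 100.

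At 1.0 to 1.1 per month the mean main cut falls at month 70 to 78. This agrees with the Amendment 8 statement that "NN expects to have completed the main phase with 50 patients with 50 EDs and V9 by Q3 2020", which is months 72 to 75.

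| Mean estimate | Interim | Main report | LPLV | Rise from interim to LPLV within a scenario |
|---|---|---|---|---|
| Crude, all data | 26.9–31.5% | 27.5–31.8% | 28.7–32.3% | 0.4–2.5 points |
| Crude, main phase only | 26.7–29.4% | 27.4–29.6% | 28.7–29.9% | 0.4–2.1 points |
| Kaplan-Meier at ED 50 | 29.5–30.1% | 29.5–30.1% | 29.5–30.1% | 0.0–0.3 points |

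The all-data row mixes the cut-off effect with true late incidence in the scenarios that assume late risk. The main-phase row largely leaves late incidence out, so it isolates the cut-off effect better.

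At the main report the denominator averaged 68 to 74, with 7 to 11 inhibitor-free children at 10 to 49 EDs and 30 to 33 children beyond 100 EDs. At the first two cuts the exact limit covered the true 50-ED risk in 93.6 to 99.2% of runs, and the Kaplan-Meier limit in 97.7 to 98.9%.

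A separate, simpler simulation with a true 50-ED risk of 30% gave crude means of 27.6 to 29.7% and Kaplan-Meier means of 29.8 to 30.2%.

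**Step 4: scale.** For 15/50 = 30.0%, the exact upper limit is 44.6%, which is 14.6 points above the estimate.

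**The case against.** The strongest reply is that 16.3 is a deliberate, fully specified observed proportion. It never claims to be a risk by ED 50. The floor removes children with little exposure who would dilute the rate, and early cases are kept. There is no test, margin, comparator or planned comparison between reports, and the 30% figure belongs to the enrolment-hold rule, not to 16.3. The shifts are small beside a 14.6-point interval arm, and the inputs that set their size are assumed. Between the main report and LPLV, the ends of the all-data ranges move by only 1.2 and 0.5 points. The separate main-phase presentation also caps exposure near ED 50. The bleeding-rate offset is only a loose parallel, since it handles recurrent counts per unit time.

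Most of this stands, and it limits the point to an improvement. Two things remain. The main-phase presentation caps the upper end but leaves the 10-ED floor, and 16.3 does not say which presentation is primary.

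Two stronger readings are tempting. A reader might infer from the 93.6% coverage that the planned limit is invalid. It is not: that coverage is measured against a 50-ED target that 16.3 does not set.

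A reader might also infer that children positive in the mandatory Visit 1 pre-dose sample (Amendment 2) would be counted as product-induced inhibitors. The documents do not support treating this as a flaw. Section 6.4 withdraws these children, and Section 3.3 requires two consecutive positive central tests. Miscounting would need dosing before the result and a second positive at the end-of-trial visit. The immunogenicity objective in 4.1 and the documented exclusions required by 16.2 would then lead analysts to a sensible exclusion.

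**Conclusion.** The point holds as an optional improvement. The primary rate is a crude proportion with a 10-ED floor. It is not a risk by a stated number of EDs, and its exposure basis differs between the interim, main and final reports. Under the assumptions shown, the shift from interim to LPLV is about 0.4 to 2.5 points on all data, part of it true late incidence where late risk is assumed. Direction and rough size agree across two onset curves, but the exact figures depend on onset, accrual, ED rates, titre split and late risk, none of which the documents give. Section 16.3 remains usable as written. Section 16 allows for a separate SAP, which is not in the file; if it already contains an ED-specific estimate, the sponsor need only confirm that.

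**What to change.** In Section 16.3, keep the exact binomial rate, state which data period it covers, and add:

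> As a supplementary analysis, cumulative incidence of first confirmed inhibitor (two consecutive positive central tests, ≥0.6 BU) will be estimated by Kaplan-Meier on the ED scale in all patients exposed to N8-GP (SAS, without the 10-ED floor), censored at the last inhibitor test, and reported at 50 and 100 EDs with a 1-sided 97.5% upper limit (complementary log-log) and number at risk.

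Apply the same to the high-titre rate in 16.4.2.3. The population must be named. Carrying the floor into the Kaplan-Meier estimate would drop early negatives while keeping early cases, a slight upward bias of at most 0.3 points in a check.

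The cost is a short addition to the wording and a few tables from data already collected. The downsides are wide limits at 100 EDs (about 30 to 33 children at risk at the main report under these assumptions), the assumption that censoring is unrelated to inhibitor risk, and a population slightly different from that of the crude rate.
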